### **3.3 Inclusion of Women and Minorities**

Both men and women of all races and ethnic groups are eligible for this trial.

## **4. REGISTRATION PROCEDURES**

### **4.1 General Guidelines for DF/HCC Institutions**

Institutions will register eligible participants in the Clinical Trials Management System (CTMS) OnCore. Registrations must occur prior to the initiation of protocol therapy. Any participant not registered to the protocol before protocol therapy begins will be considered ineligible and registration will be denied.

An investigator will confirm eligibility criteria and a member of the study team will complete the protocol-specific eligibility checklist.

Following registration, participants may begin protocol therapy. Issues that would cause treatment delays should be discussed with the Overall Principal Investigator (PI). If a participant does not receive protocol therapy following registration, the participant’s registration on the study must be canceled. Registration cancellations must be made in OnCore as soon as possible.

#### 4.2 Registration Process for DF/HCC Institutions

DF/HCC Standard Operating Procedure for Human Subject Research Titled *Subject Protocol Registration* (SOP #: REGIST-101) must be followed.

### 5. TREATMENT PLAN

#### 5.1 Treatment Regimen

Forty-five participants will participate in this open-label, single arm phase II study assessing PFS in patients TNBC and brain metastasis. Participants will receive stereotactic radiation in combination with Atezolizumab (1200mg IV) on day 1 of each 21-day (3 week) cycle. The first dose of Atezolizumab will be administered 2-7 days prior to beginning stereotactic radiation. Treatments will be administered on an outpatient basis.

Regimen Description					
Agent	Premedication; Precautions	Dose	Route	Schedule	Cycle Length
Atezolizumab	Not routinely necessary unless prior infusion reaction.	1200 mg	IV The initial dose of atezolizumab will be delivered over 60 (± 15) minutes. If the first infusion is tolerated, the second infusion may be delivered over 30 (± 10) minutes. If the 30-minute infusion is well tolerated, all subsequent infusions may be delivered over 30 (± 10) minutes.	Day 1, q3w	21 days (3 weeks)

## 5.2 Pre-Treatment Criteria

Laboratory results must be reviewed prior to dosing. If screening assessments were completed within 1 week of Cycle 1 Day 1, these assessments do not need to be repeated.

### 5.2.1 All Cycles, Day 1

- absolute neutrophil count  $\geq 1,000/\text{mcL}$
- platelets  $\geq 75,000/\text{mcL}$
- AST(SGOT)/ALT(SGPT)  $\leq 2.5 \times$  institutional ULN or  $\leq 5 \times$  institutional ULN for participants with documented liver metastases
- creatinine  $\leq 1.5 \times$  institutional ULN

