**Table 2 Dose Modification Guidelines for Hepatotoxicity**

Toxicity	Description	Management
LFT and/or total bilirubin abnormalities	Grade 1	
 
Continue Atezolizumab and monitor labs according to study calendar
 

	Grade 2	
 
Continue Atezolizumab and monitor LFTs more frequently until return to baseline or Grade ≤1
 
If persistent > 5 days, hold atezolizumab, and start prednisone 60 mg/day or equivalent. When LFTs improve to Grade ≤1 taper steroids over ≥1 month
 
When LFTs improve to Grade ≤1 and the steroid dose is prednisone ≤ 10 mg/day or equivalent (if initiated), restart atezolizumab
 

	Grade 3 or 4	
 
Permanently discontinue atezolizumab, start prednisone 60 mg/day or equivalent and inform the PI               
 
If the subject was unequivocally deriving clinical benefit, the subject may be able to resume Atezolizumab as determined by the PI.
 
 
 
If LFT results do not decrease within 48 hours after initiation of systemic steroids, consider addition of an alternative immunosuppressive agent (e.g., mycophenolate) to the corticosteroid regimen
 
Consider obtaining a hepatology consult and liver biopsy.
 
 When LFTs improve to Grade ≤1 taper steroids over ≥1 month

---

IV=intravenous; LFT=liver function test; TNF $\alpha$ =tumor necrosis factor alpha; ULN=upper limit of normal.

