## 10. STUDY CALENDAR

Screening evaluations are to be conducted within 28 days prior to initiating protocol therapy unless otherwise specified. Screening assessments occurring within 1 week prior to initiating study treatment do not need to be repeated on Cycle 1 Day 1.

Screening laboratory assessments must be done within 8 days prior to initiating protocol therapy. For women of childbearing potential, as defined in the eligibility criteria, a pregnancy test must be completed within 8 days prior to initiating protocol therapy. If a urine pregnancy test is positive or cannot be confirmed as negative, a serum pregnancy test will be required.

If the participant’s condition is deteriorating, laboratory evaluations should be repeated within 48 hours prior to initiation of the next cycle of therapy.

Assessments must be performed prior to administration of any study agent. Study assessments and agents should be administered within  $\pm$  3 days of the protocol-specified date, unless otherwise noted.

Day	Screening	Cycle 1			Cycle 2		Cycle 3	Cycle 4+		Cycle 5	Cycle 6		Off-Treatment g	Follow-Up
	Day -28 to day -1	Day 1	RT Day 1	10 days after RT	Day 1	Day 15-21	Day 1	Day 1	Day 15-21	Day 1	Day 1	Day 15-21		
Informed consent	X													
SRS Planning Appointment h	X													
Medical history b	X													
Physical exam c	X	X			X		X	X		X	X		X	
Radiation Oncologist Visit d			X d	X d										
Adverse event evaluation	X	X			X		X	X		X	X		X	
Vital signs e	X	X			X		X	X		X	X		X	
Weight	X	X			X		X	X		X	X			
Concurrent medications f	X	X			X		X						X	
ECOG Performance status	X	X			X		X	X		X	X		X	
Neurological Assessment	X	X			X		X						X	
Brain MRI e	X					X			X			X	X	X
CAP CT and/or MRI h	X					X			X			X	X	X
Hematology panel i	X	X			X		X						X	
Chemistry panel j	X	X			X		X						X	
TSH k	X	X			X		X	X		X	X			
Pregnancy test l	X													
Research Blood - cfDNA m		X	X				X	X m		X m	X m		X	X

Research Blood - Immune Markers a	X	X	X				X	X n		X n	X n		X	
Research Biopsy o	X				X								X	
Cerebrospinal Fluid Collection p	X					X							X	
Questionnaire q		X					X	X		X	X		X	X
General Impression Worksheet t	X				X		X	X		X	X			
Archival Tissue Collection	X													

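### From Cycle 4 the study calendar schedules no on-treatment hematology or chemistry panel, although Section 5.2.1 sets laboratory criteria for Day 1 of every cycle and the Grade 1 liver rule points to the calendar

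*Combined protocol and SAP*

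**What the plan says.** Section 5.2 makes laboratory review a condition of dosing: "Laboratory results must be reviewed prior to dosing". The criteria stand under the heading "5.2.1 All Cycles, Day 1" and cover "absolute neutrophil count", platelets, AST/ALT (with a separate limit for patients with liver metastases) and creatinine. The one exemption from repeat testing is for screening assessments done within a week of Cycle 1 Day 1.

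Atezolizumab is given on Day 1 of each 21-day cycle (Sections 5.1 and 10), and Section 5.5 sets no maximum number of cycles.

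In the Section 10 calendar, the rows "Hematology panel" and "Chemistry panel" are marked at Screening, Day 1 of Cycles 1, 2 and 3, and Off-Treatment. Footnotes i and j list the analytes in each panel and give no frequency.

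Table 2 in Section 6.1.1.2 gives this instruction for a Grade 1 liver test abnormality: "Continue Atezolizumab and monitor labs according to study calendar".

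**The concern.** Two operative parts of the protocol give different testing schedules for the same visits. Section 5.2.1 needs hematology and chemistry results at every dosing visit. The calendar, which sites commonly use to plan visits and orders, schedules neither panel at any dosing visit from Cycle 4. Table 2 adds to the conflict because its Grade 1 row takes its monitoring schedule from the calendar.

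At stake is whether results are to hand when a Cycle 4 or later dose is due, and whether a mild liver test rise has planned follow-up. The protocol lists hepatitis/transaminitis among expected reactions (Section 2.3.2.2), makes certain liver findings events of special interest (Section 7.1.3.1), and ties a dosing rule to the grade of hyperglycemia (Table 4). All of these draw on analytes in the chemistry panel. The 6- and 12-month safety objective (Section 1.4.1) and the summary of toxicity by maximum grade (Section 13.7) could also rest on uneven laboratory data if sites followed different parts of the protocol.

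**Working it through.** The plan gives no figure to reproduce. The check sets the calendar rows side by side and then looks for text that would fill the blank cells.

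**Step 1. Calendar rows (Section 10), on-treatment Day 1 columns and Off-Treatment.**

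| Row | C1 | C2 | C3 | C4+ | C5 | C6 | Off-Treatment |
|---|---|---|---|---|---|---|---|
| Atezolizumab | X | X | X | X | X | X | – |
| Hematology | X | X | X | – | – | – | X |
| Chemistry | X | X | X | – | – | – | X |
| Physical exam, ECOG | X | X | X | X | X | X | X |
| TSH | X | X | X | X | X | X | – |
| Concurrent medications | X | X | X | – | – | – | X |
| Neurological assessment | X | X | X | – | – | – | X |

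The panels are scheduled at 3 of the 6 dosing columns shown, and at 0 of the 3 from Cycle 4. Section 5.2.1 applies at all 6.

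**Step 2. Is this a table-reading error?** Each row above has entries for all 14 calendar columns. Physical exam, ECOG and TSH keep their Cycle 4 to 6 marks, and the Off-Treatment marks of both panels fall in the right column. Loss in conversion from PDF is unlikely but cannot be fully excluded.

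**Step 3. Does other text supply the later visits?**
- Footnotes i and j: analytes only. Footnote k, by contrast, gives TSH its own rule from Cycle 4.
- Section 10 introduction: repeat laboratory tests within 48 hours before the next cycle, but only for a deteriorating participant.
- Section 6.1.1.2: immediate liver tests, reviewed before the next dose, for patients with specified symptoms.
- Table 2: more frequent liver tests at Grade 2, and separate instructions at Grades 3 and 4.

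All of these are conditional. None sets a routine schedule from Cycle 4.

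**Step 4. Grade 1 liver abnormality.** Table 2 points to the calendar, and from Cycle 4 the calendar's next chemistry panel is at Off-Treatment.

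**Step 5. Rough size.** Cycle 4 Day 1 falls 3 × 3 = 9 weeks after the first dose, or 63 / 30.44 = 2.07 months. Assuming exponential PFS at the two medians in Section 13.2:
- median 2 months: 0.5^(2.07/2) = 0.49, or 0.49 × 45 ≈ 22 patients;
- median 3.5 months: 0.5^(2.07/3.5) = 0.66, or 0.66 × 45 ≈ 30 patients.

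These are patients still progression-free, which is only a proxy for patients still being dosed. Section 5.5 allows treatment past RANO-BM or RECIST progression, and some patients stop earlier for other reasons.

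**The case against.** The strongest reply is that the requirement is in the protocol and missing only from a summary grid. Section 5.2.1 is unconditional, and a site cannot satisfy it without results, so sites may well draw the tests whatever the calendar shows. The grid is also loose elsewhere. The concurrent medications and neurological assessment rows stop at Cycle 3 too, although footnote f carries medication recording to 30 days after the last dose and footnote c includes a neurological exam at later Day 1 visits. TSH is marked at Cycle 5, although footnote k names Cycles 4, 6 and 8. This pattern suggests a drafting lapse rather than a decision to stop testing.

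Most of that stands, and it limits the consequence. It does not remove the conflict: the two schedules differ, and Table 2 gives the calendar operative force for Grade 1 abnormalities.

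A reader might go further and infer that immune hepatitis would be missed, or that all liver monitoring defers to the calendar. The documents support neither. The dosing criteria apply at every cycle, including to Grade 1 patients. Patients are assessed clinically around each infusion (Section 6.1.1), and physical exam and adverse event evaluation are marked at Cycles 4 to 6. Grade 2 and higher abnormalities, symptomatic patients and deteriorating patients each have their own instructions. Only the Grade 1 row defers to the calendar.

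**Conclusion.** The contradiction is real, and nothing in the documents resolves it. From Cycle 4 the calendar schedules neither panel at any on-treatment visit, while Section 5.2.1 sets criteria that depend on both. A site working from the calendar could reach a dose without those results, and a Grade 1 liver abnormality would have no calendar-scheduled chemistry until Off-Treatment. Omitted testing is a risk, not a demonstrated outcome.

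Every dose from week 9 onward is affected. The 49% to 66% progression-free at that time rests on an exponential assumption and indicates only roughly how many patients might still be on treatment; it does not count omitted tests. The dose-limiting toxicity window closes at Cycle 3 Day 1, within the visits where both panels are marked, so the safety run-in is covered. Sample size, power and the primary analysis are unaffected. The conclusion assumes that the blank cells are blank in the source document.

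**What to change.** Reconcile three places so that they state one testing schedule from Cycle 4: the hematology and chemistry rows of the Section 10 calendar, Section 5.2.1, and the Grade 1 row of Table 2. Which schedule is adopted is a clinical decision for the sponsor and the investigator; this review does not choose between them. If frequency is to be governed by footnote, footnotes i and j should state it, as footnote k does for TSH.

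In the same pass, check the concurrent medications row against footnote f and the neurological assessment row against footnote c.

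The documentary cost is a few edits in one amendment, with no change to the design or analysis. Any cost in extra or fewer tests depends on the schedule chosen and on what sites already do, which the documents do not show.

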### 5.2.2 Atezolizumab Administration

██████████ will provide atezolizumab. Atezolizumab will be administered by trained medical personnel at the investigational site. Treatment compliance will be monitored through documentation of study treatment administration in the subject's medical record.

Atezolizumab will be administered in clinic on day 1 (+/- 3 days) of each cycle. Patients will receive the first dose of Atezolizumab 2-7 days before the beginning of stereotactic radiation. The initial dose of atezolizumab will be delivered over 60 ( $\pm 15$ ) minutes. If the first infusion is tolerated without infusion-associated AEs, the second infusion may be delivered over 30 ( $\pm 10$ ) minutes. If the 30-minute infusion is well tolerated, all subsequent infusions may be delivered over 30 ( $\pm 10$ ) minutes. No premedication will be allowed for the first dose of Atezolizumab. Premedication may be administered for Cycles  $\geq 2$  at the discretion of the treating physician. The management of infusion-related reactions (IRRs) will be according to severity as follows:

- In the event that a patient experiences a mild (NCI CTCAE Grade 1) IRR, the infusion rate should be reduced to half the rate being given at the time of event onset. Once the event has resolved, the investigator should wait for 30 minutes while delivering the infusion at the reduced rate. If tolerated, the infusion rate may then be increased to the original rate.
- In the event that a patient experiences a moderate IRR (NCI CTCAE Grade 2) or flushing, fever, or throat pain, the infusion should be immediately interrupted and the patient should receive aggressive symptomatic treatment. The infusion should be restarted only after the symptoms have adequately resolved to baseline grade. The infusion rate at restart should be half of the infusion rate that was in progress at the time of the onset of the IRR.
- For severe or life-threatening IRRs (NCI CTCAE Grade 3 or 4), the infusion should be stopped immediately, and aggressive resuscitation and supportive measures should be initiated. Patients experiencing severe or life-threatening IRRs will not receive further infusion and will be further managed as clinically indicated until the event resolves.

For anaphylaxis precautions, see APPENDIX B.

### 5.2.3 Other Modality(ies) or Procedures

#### 5.2.3.1 Stereotactic radiation

##### 5.2.4.1.1 Timing of Radiation

Radiation must begin within 14 days after brain MRI obtained with T1 post contrast sequences, with a maximum slice thickness of 1.5mm. Radiation must be delivered at Brigham and Women's Hospital or Dana-Farber Cancer Institute.

##### 5.2.4.1.2 Dose

Lesions <2 cm in maximum diameter will be treated with stereotactic radiosurgery, generally 20 Gy in 1 fraction. Lesions between 2.0 and 2.5 cm in maximum diameter will generally be treated to 18 Gy in 1 fraction. Lesions between 2.5-3.0 cm in maximal diameter will generally be treated with stereotactic radiotherapy to 30 Gy in 5 fractions given on consecutive weekdays. The volume receiving 12 Gy (V12) should be limited to <8-10cc; dose reductions are acceptable if the V12 constraint cannot be met via replanning, with a minimum dose of 16 Gy. Patients with simultaneous metastases that require 1 fraction and 5 fractions can be treated concurrently. If a metastasis that would be treated normally with stereotactic radiosurgery is adjacent to a metastasis that must receive stereotactic radiotherapy (so that a significant degree of scatter dose from the latter field will include the potential former field) it is acceptable for the treating investigator to treat both metastases with stereotactic radiotherapy.

The treating radiation oncologist may use their discretion in the best interest of the patient in the treating participants on study.

##### 5.2.4.1.3 Physical Factors

Treatment will be delivered using megavoltage machines with 6MV photon beams using a linear accelerator equipped with stereotactic capabilities.

##### 5.2.4.1.4 Simulation, Immobilization, and Localization

The patient will be treated in the supine position. A tightly fitting thermoplastic mask will be employed for immobilization.

##### 5.2.4.1.5 Treatment Planning and patient setup

The gross tumor volume (GTV) will cover the metastasis as identified by contrast enhanced MRI and CT (contrast optional) obtained within 14 days of the treatment initiation date. The MRI must be obtained with a T1 post contrast sequence with a maximal slice thickness of 1.5 mm. No clinical target volume (CTV) is to be used. The planning target volume (PTV) will be 1 mm. For patients who have rapidly growing gross disease an extra 0.1-1mm of PTV margin can be added at the discretion of the treating clinician to account for growth between planning and treatment; in such cases the time between planning and treatment should be minimized to the greatest extent

possible. Treatments will be delivered through volumetric modulated arc therapy (VMAT) using a single isocenter for PTV volumes >1.5 cm in maximum diameter. For PTV volumes with a maximum dimension of 0-1.5 cm in diameter either VMAT, circular collimators, or multiple static fields will be acceptable. The prescription will generally be normalized to the 60-95% isodose line. The maximum allowed hot spot will be 170%. 100% of the GTV should be covered by the prescription dose. At least 99% (ideal) / 98% (at minimum) of the PTV should be covered by the prescription isodose line. The entire PTV should be covered by 90% (ideal) / 85% (at minimum) of the prescription dose. Daily set up with cone beam CT or stereoscopic KV imaging is mandated.

#### 5.2.4.1.6 Dose to Critical Structures

Dose constraints for stereotactic radiation to critical structures will be as follows:

#### Dose constraints for stereotactic radiation

Organ at Risk	Tolerance	Dose Modification Regimen
Eyes, Optic Nerves, Optic Chiasm	Point dose $\leq 8$ Gy	If point dose >8 Gy, undercover PTV while maintaining 100% GTV coverage. If not achievable, dose reduce GTV to highest dose which meets optic constraint, through 16 Gy (15 Gy for cavity in which gross total resection has been achieved). If 100% of GTV cannot be safely covered by 16 Gy (15 Gy for cavity in which gross total resection has been achieved), then an acceptable variation will be to convert to stereotactic radiotherapy – see Table 2
Brainstem (defined as brainstem volume minus GTV)	Dose to 0.035cc $\leq 12$ Gy	If dose to 0.035cc >12 Gy, undercover PTV while maintaining 100% GTV coverage. If not achievable, dose reduce GTV to highest dose which meets brainstem constraint, through 16 Gy (15 Gy for cavity in which gross total resection has been achieved). If 100% of GTV cannot be safely covered by 16 Gy (15 Gy for cavity in which gross total resection has been achieved), then an acceptable variation will be to convert to stereotactic radiotherapy – see Table 2
Volume of normal brain (less the GTV) receiving >12 Gy (per individual lesion, called the V12)	$\leq 10$ cc	If the V12 is >10cc, undercover PTV while maintaining 100% GTV coverage. If not achievable, dose reduce GTV to highest dose which meets constraint, through 16 Gy (15 Gy for cavity in which gross total resection has been achieved). If 100% of GTV cannot be safely covered by 16 Gy (15 Gy for cavity in which gross total resection has been

		achieved), then an acceptable variation will be to convert to stereotactic radiotherapy – see Table 2
Normal brain less the GTV (for entire brain)	Mean <5 Gy	Administer stereotactic radiation on two or more consecutive weekdays rather than a single day

Dose constraints for stereotactic radiotherapy to critical structures will be as follows:

**Dose constraints for stereotactic radiotherapy (5 fractions)**

Organ at Risk	Tolerance	Dose Modification Regimen
Eyes, Optic Nerves, Optic Chiasm	Point dose of 25-27 Gy	If point dose >25-27 Gy undercover PTV while maintaining 100% GTV (30 Gy in 5 fractions if gross disease; 25 Gy in 5 fractions if gross total resection has been achieved) coverage. If not achievable, dose reduce GTV to highest dose which meets constraint, through 23 Gy in 5 fractions. 100% of GTV should always receive at least 23 Gy in such a scenario.
Brainstem (defined as brainstem volume minus GTV)	Dose to 0.035cc ≤28 Gy	If dose to 0.035cc >28 Gy, undercover PTV while maintaining 100% GTV coverage (30 Gy in 5 fractions if gross disease; 25 Gy in 5 fractions if gross total resection has been achieved). If not achievable, dose reduce GTV to highest dose which meets brainstem constraint, through 23 Gy in 5 fractions. 100% of GTV should always receive at least 23 Gy in such a scenario.

5.2.4.1.7 Stereotactic Radiation Documentation Requirements

The institution will archive treatment prescription and verification images for later review by the study chair if requested. At least one port film or pretreatment alignment film/CT along with the digitally reconstructed radiographs (DRRs) from the treatment planning program or, alternatively, a simulation verification radiograph shall be acquired and kept for evaluation if requested except where geometrically impractical.

5.2.4.1.8 Stereotactic Radiation Radionecrosis Assessment

To assess participants for potential delayed radiation toxicity, a radiation follow-up visit will be performed approximately 6 months after completion of stereotactic radiation treatment. This visit should be done no earlier than 5 months and no later than 8 months post-stereotactic radiation. Another visit should occur, if possible, around 12 months after completion of radiation treatment. This visit should be performed no earlier than 11 months and no later than 14 months post-radiation. At these timepoints, brain imaging will be correlated with a clinical assessment,

performed by the radiation oncology team. All potential radiation necrosis events will be adjudicated by the PI, [name], in collaboration with the trial radiation oncologist, [name]. A diagnosis of radiation necrosis will be ascribed if:

1. Surgery on an enlarging lesion after radiation reveals a specimen showing predominantly necrosis
  2. Changes consistent with necrosis on dual-phase PETCT are seen
  3. Changes consistent with necrosis on serial MRI studies of the brain are seen.
- Changes consistent with necrosis on serial MRIs of the brain included lack of sustained growth over time in patients who did not receive central nervous system-active systemic therapy after initial enlargement, development of a non-distinct margin of enhancement on T1 post contrast sequences, development of a hypointense center on T1 post contrast images, and a large edema to enhancement ratio.

If a diagnosis of radiation necrosis is made for any patient in this cohort, we will distinguish radiographic necrosis from radiographic and symptomatic necrosis based upon the presence versus absence of associated neurologic symptoms or administration of dexamethasone / bevacizumab for neurologic symptomatology correlating with the anatomic location of the lesion in question.

Every attempt should be made for these assessments to occur in person. Due to the nature of this patient population, some participants may be on hospice or otherwise not able to travel to the study site to complete these endpoints. In these cases, the study team will check to see if any brain imaging has been completed at local facilities and will obtain those images for review. The radiation team may reach out to the patient to perform the radiation necrosis assessment over the phone. Not completing these visits in person will not constitute protocol violations.

